## SCHEDULE OF EVENTS - CONTROL GROUP (Corticosteroid)

Description	Visit 1 (Baseline)	Visit 2 (12 Week)	Visit 3 (24 Week)
Study Visit Windows			
Informed Consent	x		
Complete Physical & Medical History	x		
Knee Assessment/Brief Exam	x		
Ultrasound	x	x	x
Aspiration and Steroid Injection	x		
Visual Analogue Score	x	x	x
Knee Injury and Osteoarthritis Outcome Score	x	x	x
Rauschning and Lindgren criteria	x	x	x

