An ultrasound guided aspiration and triamcinolone (40 mg) diluted with lidocaine without epinephrine and ropivacaine will be used to anesthetize the tissues down to the cyst(including within the cyst for steroid injections). A compression bandage will be placed locally for 7 days. Investigators will monitor any side effect from the injection and treat the patients per standard care, this can include prescription of analgesics.

Both groups will be asked to have a follow up after 3 months and 6 months of the day of the procedure with measurements of the dimensions of the baker's cysts with ultrasound, Visual Analogue Score, and Rauschning and Lindgren criteria and reclassification.

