## III. Data Safety Monitoring Plan (DSMP)

### I. Description of the types of data or events that will be captured

#### a. SAFETY information to be collected

All disease signs and symptoms experienced by the patient, as defined below as AE, TEAE, SAE, and UADE, will be recorded from questionnaires during each visit and clinic visits. Specific information collected about the adverse event will include the nature, date and time of the event. There will also be a determination of seriousness, frequency, severity, corrective treatment, outcome, and the principal investigator's opinion of the relationship to the Ultrasound guided aspiration and injection of either Corticosteroid or Platelet-Rich-Plasma. Documentation will begin at the time the patient signs the informed consent form to the completion of the final study visit.

- Adverse Event (AE)

An AE is any untoward or unfavorable medical occurrence in a patient involved in a study associated with the use of a medical treatment or procedure regardless of whether it is considered related to the treatment or procedure. AEs therefore include any undesirable physical, psychological or behavioral effect experienced by a subject during their participation in this investigational study, whether or not the effect is considered interrelated.

The Principal Investigator will assess relationship between the AE and study treatment according to the following definitions:

- Unrelated: There is no relationship between the AE and the use of the investigational device or any study treatment. This may include but is not limited to the incident being an expected outcome of a previously existing or concurrent disease, concomitant medication or procedure the patient experienced.
- Remote/unlikely: There is no clear relationship between the AE and the use of the device under investigation or study treatment and it is unlikely that there is some relationship.
- Possible: There is no clear relationship between the AE and the use of the study device or study treatment; however, one cannot definitely conclude that there is no relationship.

- Probable: While a clear relationship to the device under investigation or study treatment cannot be established, the AE is associated with an expected AE or there is no other medical condition or intervention, which could explain the occurrence of such an event.

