- Definite: The relationship of the AE and the use of the study device or the execution of the study treatment can definitely be established.

- Treatment Emergent Adverse Event (TEAE)

A TEAE is defined as any event not present prior to the initiation of the treatment or any event already present that worsens in either intensity or frequency following exposure to the treatments. The assessment of TEAEs and their relationship to the study treatment will be assessed by the Principal Investigator.

- Serious Adverse Event (SAE)

A SAE is defined as any AE, irrespective of a possible relationship to the study device that results in any of the following outcomes:

- Death
- Life-threatening event
- Requires inpatient hospitalization or prolongation of existing hospitalization
- Results in persistent or significant disability/incapacity
- Congenital anomaly
- An important medical event defined as an AE that may jeopardize the subject and may require medical or surgical intervention in order to prevent one of the outcomes listed above

- Unexpected Adverse Device Effect (UADE)

A UADE is defined as any serious adverse effect on health or safety or any life-threatening problem or death caused by, or associated with, a device, if that effect, problem, or death was not previously identified in nature, severity, or degree of incidence in product labeling, the investigational plan or application (including a supplementary plan or application), or any other unanticipated serious problem associated with the study device that relates to the rights, safety, or welfare of subjects (21 CFR 812.3(s)).

b. Clinical Outcomes of Platelet Rich Plasma Injection versus Corticosteroid Injection for Baker's Cyst, information to be collected

- History and physical exam of the patient
- History and physical exam of the study lower extremity
- Concomitant medications
  - Type
  - Dose
  - Frequency
  - Duration
- Patient Outcomes Assessments
  - Visual analog scale (VAS) for rating activity-related pain
  - Rauschning and Lindgren criteria for rating clinical presence of Baker's cyst
  - Knee Injury and Osteoarthritis Outcome Score (KOOS) for rating outcome of knee related conditions
    - Ultrasound of Study Lower extremity
- Reportable and/or adverse events

II. Plan for assuring data accuracy and protocol compliance

Study Monitor

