## 5. RISKS AND BENEFITS

### I. Risks:

Subjects involved in the study will be at risk of complications associated with the injection such as pain at the site of the injection, infection, bleeding or hematoma formation.

Subjects in the Corticosteroid group: Studies have shown that corticosteroid injection into soft tissues is safe, and no serious unexpected reactions have been reported. In general, corticosteroid injection into the cyst may result in local atrophy and post injection flare but the use of Triamcinolone lowers the frequency of these complications from happening due to its pharmacological characteristics.

Subjects in the PRP group: Although There has been no data about using PRP into a baker's cyst, studies have stated that the side effects of Platelets-Rich-Plasma injections in soft tissues are very limited as the patients are utilizing their own blood. The main risk includes local infection (less than 1%) and flare reaction beginning the day after the injection.

Breach of confidentiality is an unlikely, but possible risk to subjects included in this study.

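### No scheduled examination or predefined item after injection targets local atrophy, a named steroid-arm risk; the brief knee exam is ticked at baseline only

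*Combined protocol and SAP*

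**What the plan says.** The two Schedules of Events agree with each other. The rows "Complete Physical & Medical History" and "Knee Assessment/Brief Exam" are marked at Visit 1 only, in the corticosteroid arm and in the PRP arm. Ultrasound, VAS, KOOS and the Rauschning and Lindgren grade are marked at all three visits. Neither schedule has an adverse-event row.

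Section 5.I (Risks) lists injection-site pain, infection, bleeding and hematoma for all subjects. For the steroid arm it adds that "corticosteroid injection into the cyst may result in local atrophy and post injection flare", while saying that the choice of triamcinolone makes these less frequent.

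Safety capture is described in three places:

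- Section 4.I, for each arm: "Investigators will monitor any side effect from the injection and treat the patients per standard care". Section 5.II makes a similar commitment for each arm.
- Section 4.III (Data Safety Monitoring Plan), part I.a: "All disease signs and symptoms experienced by the patient", within the listed event categories, "will be recorded from questionnaires during each visit and clinic visits". On the period covered: "Documentation will begin at the time the patient signs the informed consent form to the completion of the final study visit".
- The same plan, part I.b, lists "History and physical exam of the study lower extremity" among the information to be collected, with no visit attached.

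Aims 3 and 4 (section 2.IV) are to evaluate complications and side effects.

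**The concern.** Local atrophy is a physical sign at the injection site, and here the site is behind the knee. The only examination that the schedules provide is a baseline one, at the same visit as the injection, so it cannot show an effect that develops afterwards. No later scheduled item asks about atrophy.

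Two of the four aims depend on complete recording of harms. If a harm named for one arm is recorded only when somebody happens to notice it and report it, the count for that arm may be too low. A blank entry also cannot be told apart from a true absence. The protocol describes blinding of patients but not of those who assess them, so unstructured detection could differ between arms.

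**Working it through.** The plan gives no figure for this point, so the check is mainly a reading of one section against another.

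**1. What each item scheduled at weeks 12 and 24 covers**

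| Item | Stated content (section 4.I) | Atrophy item stated? |
|---|---|---|
| Ultrasound | Cyst dimensions | No |
| VAS | Pain (activity-related, per section 4.III, I.b) | No |
| KOOS | Pain, other symptoms, daily living, sport and recreation, quality of life | No |
| Rauschning and Lindgren grade | Swelling, pain or tension, limitation of motion | No |
| Brief knee exam | Not scheduled after baseline | – |
| Full physical and history | Not scheduled after baseline | – |

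**2. What the unscheduled provisions add.** The monitoring commitment in sections 4.I and 5.II has no stated method, visit or form. The capture in section 4.III, I.a, is broad: it covers signs as well as symptoms, includes clinic visits, and runs to the last visit. But its questionnaires are not identified, and neither an injection-site inspection nor a definition of atrophy is given. Atrophy could be recorded by these routes, but none of them requires anyone to look for it.

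**3. The leg exam in section 4.III, I.b.** It has no visit. It may be the same item as the brief knee exam, and so baseline only, or it may be meant for every visit. The text does not settle this.

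**4. Size.** Inputs: 50 patients, 25 per arm (sections 3.I and 4.I); 2 follow-up visits (schedules); full attendance assumed.

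- Follow-up visits without a scheduled exam: 50 × 2 = 100, of which 25 × 2 = 50 are in the steroid arm.
- Effect of one missed case on the arm's rate: 1/25 = 4 percentage points.
- Expected cases if the true atrophy rate were 2% to 10% (an assumption, since the documents give none): 25 × 0.02 = 0.5 to 25 × 0.10 = 2.5.
- Chance that at least one steroid patient is affected, 1 − (1 − r)^25: at r = 0.02, 1 − 0.98^25 = 0.40; at r = 0.10, 1 − 0.90^25 = 0.93.
- Value of a recorded absence: if all 25 steroid patients were checked and none had atrophy, the one-sided 95% upper limit for the rate would be 1 − 0.05^(1/25) = 0.113, or about 11%. Without recorded absences, no such statement can be made.

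**The case against.** The strongest reply is that the plan does provide for detecting side effects. Safety capture extends to all signs and symptoms and takes in clinic visits as well as questionnaires. Investigators undertake in both arms to monitor effects of the injection, and section 5.II makes that undertaking for the steroid arm directly after discussing atrophy and flare. Patients are seen at weeks 12 and 24 for ultrasound and clinical grading of the same knee, so staff could notice a visible change. Section 5 also argues that the drug and its dilution make atrophy less likely. Aims 3 and 4 speak of evaluating harms, and section 4.II plans tests on scores only, with no adverse-event comparison.

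Much of this stands. A reader might infer that adverse events come only from knee-symptom questionnaires and that atrophy is therefore never looked for. The documents do not support that: the questionnaires are not described as knee-specific, clinic visits are named as well, and general monitoring is promised. Nor do they show that corticosteroid would be made to look safer. Under-counting is a possibility, and an assessor who knows the arm might instead look harder for atrophy in steroid patients.

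What the reply does not supply is a scheduled, uniform check. An opportunity to notice atrophy does not yield a recorded presence or absence for each patient in each arm.

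**Conclusion.** The concern holds in a limited form. After injection, no scheduled examination and no predefined item targets local atrophy. Its detection depends on general monitoring and on adverse-event capture whose instruments are not specified. This could under-count a steroid-specific harm and weakens Aims 3 and 4; it does not affect the score-based comparison. The undated leg exam in the monitoring plan and the baseline-only exam in the schedules must be reconciled.

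The exposure is 100 follow-up visits under full attendance, with 4 percentage points per missed case in an arm of 25. How many cases might be missed is unknown: the 2% to 10% range is an assumption, and at its lower end fewer than one case is expected. The conclusion rests on the schedules and the safety text, not on that range.

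It applies chiefly to atrophy. Infection, hematoma and flare may have resolved by week 12, so an examination first made then would add little for them. The change is worth making because it is cheap.

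**What to change.** - Tick the brief knee exam at Visits 2 and 3 in both schedules.
- Define an injection-site check, identical in both arms, that records local atrophy as present or absent for each patient. On the same form, record any other complication named in section 5.I that is still visible or has been reported since the last visit.
- In section 4.III, I.a, add examination of the injection site to the sources of adverse-event data.
- In section 4.III, I.b, state the visits at which the study leg is examined, consistent with the schedules.

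The cost is about a minute at visits where the same site is already scanned and the knee graded, plus one short form. No extra visit or staff is needed. A small downside is that more minor events will be recorded. The change concerns data collection only and leaves treatment as planned.

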## SCHEDULE OF EVENTS - TREATMENT GROUP (PRP)

Description	Visit 1 (Baseline)	Visit 2 (12 Week)	Visit 3 (24 Week)
Study Visit Windows			
Informed Consent	x	+/- days	+/- days

Complete Physical & Medical History	x		
Knee Assessment/Brief Exam	x		
Ultrasound	x	x	x
Aspiration and PRP	x		
Visual Analogue Score	x	x	x
Knee Injury and Osteoarthritis Outcome Score	x	x	x
Rauschning and Lindgren criteria	x	x	x

## II. Data Analysis and Monitoring

Descriptive statistics will be provided to compare baseline distribution of two groups, those who are treated by a traditional method and those who are treated by Cortisone for Baker's Cyst. Basically, we are comparing the change of scores in two groups in this study: a matched T-test (for a continuous score) or a chi-squared test (for a discrete score) or using non-parametric tests, Wilcoxon rank test and/or Kruskal-Walis test. The type of test will be decided after we check the normality of score distributions using Kolmogorov-Smirnov test or Shapiro-Wilks test.

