**III. Study Design:**

Prospective study with Randomized patients into Ultrasound-guided Platelets-Rich-Plasma injection and Ultrasound guided Corticosteroid Injection and at least 6 months follow up at our institution.

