**IV. Aims:**

- 1) To evaluate the outcome of baker's cysts with the use of Platelets-Rich-Plasma versus Corticosteroid
- 2) To evaluate the recurrence of baker's cysts treated on each group
- 3) To evaluate complications
- 4) To evaluate side effects

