**4. METHODS AND PROCEDURES****I. Methods and procedures**

Patients who meet the inclusion criteria and do not meet any of the exclusion criteria will be identified during office hours by the PI and co-investigators. Our research staff will explain the purpose of the study to the patient, and will go over the consent form, to fully inform and answer any questions the subject may have.

After patients accept to participate in the study and are formally enrolled in the study, the same day, patients will be asked the Visual Analogue Score (VAS), demographic information will be collected, along with any associated medical history with special interest in knee pathologies and previous treatments. They will be also classified according to their symptoms by the Rauschning and Lindgren criteria which are used to clinically evaluate the presence of the popliteal cysts, pain, posterior sense of tension in the popliteal fossa and its clinical importance for range of motion reduction. They will also complete the Knee Injury and Osteoarthritis Outcome Score (KOOS) to assess short and long term outcome of knee related conditions.

Rauschning and Lindgren criteria:

Grade 0: absence of swelling and pain, no limitation of range of motion

Grade 1: light swelling or a sense of posterior tension after intense activity, minimal limitation of ROM

Grade 2: swelling and pain after normal activity, ROM limitation less than 20 degrees

Grade 3: swelling and pain even when resting, ROM limitation more than 20 degrees

The Knee Injury and Osteoarthritis Outcome Score (KOOS):

- Pain
- Other Symptoms
- Function in daily living (ADL)
- Function in sport and recreation
- Knee-related quality of life (QOL)

We will blindly set 25 envelopes sealed for each group, and randomly assign one of them to each patient. Patients will then be part of either the Platelets-Rich-Plasma group or the Corticosteroid group.

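### The only parametric test named for continuous score changes is a matched t-test, which does not fit two unpaired randomised arms

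*Combined protocol and SAP*

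**What the plan says.** The whole analysis plan is one paragraph, section 4.II (Data Analysis and Monitoring). Its main sentence begins "Basically, we are comparing the change of scores in two groups in this study: a matched T-test (for a continuous score" and then offers "or a chi-squared test (for a discrete score) or using non-parametric tests, Wilcoxon rank test and/or Kruskal-Walis test". The choice among these comes later: "The type of test will be decided after we check the normality of score distributions using Kolmogorov-Smirnov test or Shapiro-Wilks test". No unpaired t-test, analysis of covariance or mixed model is named anywhere in the document.

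The design is set out elsewhere:

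- Section 2.III (Study Design): "Prospective study with Randomized patients into Ultrasound-guided Platelets-Rich-Plasma injection and Ultrasound guided Corticosteroid Injection".
- Section 2.IV (Aims), first aim: "To evaluate the outcome of baker's cysts with the use of Platelets-Rich-Plasma versus Corticosteroid".
- Section 4.I (Methods and procedures), on allocation: "We will blindly set 25 envelopes sealed for each group, and randomly assign one of them to each patient". The next sentence places each patient in one group or the other.
- Section 4.I, on the follow-up visits at 3 and 6 months: the assessments include "measurements of the dimensions of the baker's cysts with ultrasound, Visual Analogue Score". The schedules of events add KOOS.

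**The concern.** A matched (paired) t-test needs a natural pairing of observations. Two parallel arms of individually randomised patients have none between them. The document describes no matching of patients, no crossover and no use of both knees.

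The chi-squared test is assigned to discrete scores, and the Wilcoxon and Kruskal-Wallis tests are the non-parametric alternatives. So when a continuous score such as VAS or KOOS passes the normality check, the plan sends it to a test that does not suit the PRP-versus-corticosteroid comparison. Cyst dimensions would probably follow the same route, although the plan does not call them a score.

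At stake is whether the main comparison yields a between-arm difference with a confidence interval, and whether two analysts following the plan would get the same p-value. The non-parametric fallback is also unclear, because the Wilcoxon test is named without saying whether the signed-rank (paired) or rank-sum (two-sample) form is meant.

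**Working it through.** **1. The plan's own sample size treats the arms as independent.** Section 3.I (Sample Size Justification) gives one-sided alpha 0.05 and 80% power. The usual pooled formula for two independent proportions, with p̄ = (P1 + P2)/2, is

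n = [1.645·√(2p̄(1−p̄)) + 0.842·√(P1(1−P1) + P2(1−P2))]² / (P1 − P2)²

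For 0.1 v 0.4, p̄ = 0.25, so n = (1.645×0.612 + 0.842×0.574)²/0.09 ≈ 24.7, which rounds up to 25. The other two rows give 21 and 19. All three rows of the table reproduce exactly. The sizing therefore assumes unpaired arms and the analysis sentence does not.

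**Assumptions for what follows.** 25 completers per arm, two-sided 0.05 unless stated, and effects in units of the SD of change, because the documents give no SD.

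**2. Reading A: baseline versus follow-up within each arm.** The power p of one arm's paired test comes from the noncentral t with 24 df and noncentrality d·√25 = 5d. If both arms truly improve by the same d, the chance that exactly one is significant is 2p(1−p), computed here from unrounded p:

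| True change in both arms (SD) | Within-arm power | Exactly one arm significant |
|---|---|---|
| 0.2 | 0.161 | 27% |
| 0.3 | 0.302 | 42% |
| 0.4 | 0.484 | 50% |
| 0.5 | 0.670 | 44% |
| 0.6 | 0.821 | 29% |
| 0.7 | 0.919 | 15% |
| 0.8 | 0.970 | 6% |
| 1.0 | 0.998 | 0.5% |

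This is the frequency of a misleading pattern, not the error rate of a test.

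With large improvements the opposite happens. If the true changes are 0.8 and 1.6 SD, both arms are significant in 97% of trials, so the paired tests do not show the 0.8 SD difference. A two-sample t-test (48 df, noncentrality 0.8·√12.5 = 2.83) detects it in 79%.

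**3. Reading B: pairing patients across arms.** With unrelated pairs the noncentrality is the same, d·√(n/2), but the df fall from 48 to 24, so the two-sided critical t rises from 2.011 to 2.064.

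- Type I error: 4.9% in 200,000 simulated null trials, so it is held.
- Power at 0.8 SD, paired v two-sample: 77% v 79% two-sided; 86% v 87% one-sided, the sidedness used in section 3.I.
- Dependence on order: 400 simulated data sets were shifted so that the two-sample p was exactly 0.05, and each was re-paired at random 1,000 times. The average 2.5th, 50th and 97.5th percentiles of the paired p were 0.017, 0.056 and 0.101, and 40% of pairings fell below 0.05.
- Unequal completers (25 v 20, assumed): only 20 pairs can be formed and five patients are dropped. Power at 0.8 SD is 67% (noncentrality 0.8·√10 = 2.53, 19 df) against 74% for the two-sample test on all 45 (noncentrality 0.8·√(25×20/45) = 2.67, 43 df).

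**The case against.** The strongest defence is that change is itself a within-patient, and so matched, difference. On this reading the phrase is loose wording for a t-test on those differences, compared between arms. The sentence does state a between-group intent, so the defect would be a mislabelled test and not an absent comparison. That is a plausible account of what was meant. It does not rescue the text: a t-test comparing changes between unpaired arms is an independent-samples test, and the plan names a different one.

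Other points narrow the concern, and they stand:

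- The same sentence names Kruskal-Wallis, which with two groups is equivalent to the rank-sum test, so one valid unpaired route exists. The plan offers it as a non-parametric option, so it does not fill the gap for scores judged normal.
- The trial was sized on a difference in proportions, which matches the chi-squared route. That comparison does not use the matched test.
- The figures rest on assumed inputs. One-arm-only significance is common only for modest improvements. The re-pairing range is taken at p = 0.05, where the conclusion is most sensitive. With equal completers the power loss from cross-arm pairing is under 2 percentage points. The 67% v 74% comparison needs losses in one arm only.
- Welch rather than pooled variance, and any baseline-adjusted model, are preferences. The necessary correction is an independent two-sample test.

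**Conclusion.** The concern holds. As written, section 4.II names the wrong parametric test for a two-arm parallel trial, and none of the three readings makes the wording right. Under the within-arm reading there is no between-arm estimate or interval. Under the cross-arm reading the test is valid on average but cannot be reproduced, because no pairing rule is given. Under the loose-wording reading the name simply has to be corrected.

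The reach is limited to continuous scores that pass the normality check, plus the ambiguity over which Wilcoxon test is meant. The conclusion itself rests on the text and not on the assumed SD units, which only illustrate the consequences. This should be fixed before analysis. It does not call the design or the sample size into question.

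**What to change.** In section 4.II, replace the matched t-test with wording such as:

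> For continuous scores, change from baseline will be compared between the PRP and corticosteroid arms with an independent two-sample (Welch) t-test. The between-arm difference and its 95% confidence interval will be reported at 3 and 6 months. If a non-parametric test is used, it will be the two-sample Wilcoxon rank-sum test. Within-arm paired tests are descriptive only.

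A linear model of the follow-up score on arm and baseline score is an acceptable alternative, but is not required to correct the error.

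A separate editorial correction belongs in the same paragraph: the sentence on baseline descriptives labels the groups as a traditional method and cortisone, and never mentions PRP. The arm names should be PRP and corticosteroid.

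The cost is one reworded sentence and one editorial correction. No new data, extra patients or change in sample size is needed, since the 25 per arm already comes from a formula for independent groups.

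### The continuous outcomes are compared as unadjusted change scores although baseline VAS and KOOS are collected; adjusting for baseline would usually be more precise, by an amount the documents do not fix

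*Combined protocol and SAP*

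**What the plan says.** Section 4.II, Data Analysis and Monitoring, describes the comparison in one sentence: "Basically, we are comparing the change of scores in two groups in this study". The tests offered are "a matched T-test (for a continuous score) or a chi-squared test (for a discrete score) or using non-parametric tests", with the choice made after a normality check. No section of the protocol mentions analysis of covariance, regression or any other use of the baseline value.

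The baseline values needed for adjustment are largely there. On the day of enrolment, according to section 4.I, "patients will be asked the Visual Analogue Score (VAS), demographic information will be collected", and the same section has patients complete the KOOS. Both schedules of events tick VAS, KOOS, ultrasound and the Rauschning and Lindgren criteria at baseline, week 12 and week 24. Cyst size is less certain: section 4.I describes the follow-up visits "with measurements of the dimensions of the baker's cysts with ultrasound, Visual Analogue Score, and Rauschning and Lindgren criteria and reclassification", but its account of baseline lists no cyst measurement. The schedules tick an ultrasound at baseline without saying that dimensions are recorded.

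**The concern.** Subtracting the baseline value from the follow-up value amounts to fixing the regression slope of follow-up on baseline at 1. When the true slope is below 1, as it is with equal standard deviations and imperfect correlation, the subtraction over-corrects. An arm that happens to start worse will then tend to show more improvement, through regression to the mean. Estimating the slope removes this component. With 25 patients per arm, allocated from 25 sealed envelopes per group with no stratification described, chance baseline differences are not negligible. What is at stake is the width of the confidence intervals and the power for VAS, KOOS and cyst size, for which the protocol gives no power calculation.

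**Working it through.** **The plan's own figure.** Section 3.I takes proportions of 0.1 and 0.4, one-sided alpha 0.05 and 80% power. With pooled variance and no continuity correction:

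n = [1.645 × √(2 × 0.25 × 0.75) + 0.842 × √(0.1 × 0.9 + 0.4 × 0.6)]² / 0.3² = (1.007 + 0.484)² / 0.09 ≈ 24.7, so 25 per arm.

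The other two rows reproduce as 21 and 19, and power at 25 per arm is 80.4%. This calculation is binary, so it says nothing about precision for a continuous score.

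**Inputs for the continuous outcomes.** From the documents: 25 per arm and one-sided alpha 0.05. Assumed, because the documents are silent: correlation r between baseline and follow-up of 0.3, 0.5 or 0.7; equal standard deviations (SD) at the two times; and the t-test in section 4.II read as a two-sample test of changes.

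**Variances, in units of SD².**
- Change score: 2(1 − r)
- Baseline-adjusted: 1 − r²
- Ratio, adjusted to change: (1 + r)/2
- Patients per arm a change-score analysis needs to match adjustment at 25 per arm: 25 / ratio

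| r | Change | Adjusted | Ratio | Equivalent n per arm | Extra per arm |
|---|---|---|---|---|---|
| 0.3 | 1.40 | 0.91 | 0.65 | 38.5 | 13.5 |
| 0.5 | 1.00 | 0.75 | 0.75 | 33.3 | 8.3 |
| 0.7 | 0.60 | 0.51 | 0.85 | 29.4 | 4.4 |

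**Cost of estimating the slope.** Inflating the adjusted variance by 1 + 1/46 lowers the extra patients to 12.6, 7.6 and 3.8. A simulation of 20,000 trials with 25 per arm gave variance ratios of 0.669, 0.763 and 0.880, that is 12.4, 7.8 and 3.4 extra.

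**Where the extra variance comes from.** 2(1 − r) = (1 − r²) + (1 − r)². The last term (0.49, 0.25, 0.09) is the contribution of chance baseline imbalance. For scale, the standard error of the baseline difference is √(2/25) = 0.283 SD. An imbalance of that size moves the change-score difference by 0.283 × (1 − r) = 0.20, 0.14 or 0.08 SD. This is the precision loss seen from another side, not a second harm.

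**Power.** Suppose the change-score test had 80% power at one-sided 0.05. Its standardised effect is then 1.645 + 0.842 = 2.486. Dividing by √ratio and subtracting 1.645 gives 1.44, 1.23 and 1.05, so power of 92.5%, 89.0% and 85.4%. Charging for the slope gives 92.0%, 88.4% and 84.7%.

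**Unequal standard deviations.** With k = baseline SD / follow-up SD, the ratio is (1 − r²)/(1 + k² − 2rk). Before the slope cost:
- k = 0.8: 6.9, 3.0 and 0.5 extra per arm at r = 0.3, 0.5 and 0.7.
- k = 1.25: about 25, 19 and 15 extra per arm.
- k = r: no gain.

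In general the change-score variance exceeds the adjusted variance by (baseline SD − r × follow-up SD)², which is never negative.

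**The case against.** The strongest reply is that the planned comparison is valid and the size of the gain is unknown. Both parts stand. Under randomisation the change-score difference is unbiased and its standard error already includes chance imbalance. The correlation and the equal standard deviations are assumptions, and the gain can fall to almost nothing (0.5 per arm at k = 0.8, r = 0.7). At 25 per arm the slope must also be estimated, so the statement that change scores are never more precise is a large-sample one. None of this gives a reason to prefer the unadjusted analysis. It limits what can be claimed about the size.

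Four stronger readings are tempting, and the documents do not support them.
- A reader might infer that the estimate is biased by baseline imbalance. It is not; the imbalance is part of its variance.
- A reader might infer that the trial's sample size is wrong on this account. Section 3.I rests on a difference in proportions and reproduces on that basis.
- A reader might infer that each follow-up visit is tested separately. Section 4.II does not say how weeks 12 and 24 are handled.
- A reader might infer that every baseline value is available. For cyst dimensions that is not stated.

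A further difficulty is that the t-test is described as matched, although the arms are independent. The planned between-arm test is therefore itself unclear, and the calculation depends on the reading stated above.

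**Conclusion.** The point holds as an efficiency matter for VAS, KOOS and, if measured at baseline, cyst size. The plan does not use baseline values it already collects to sharpen these comparisons. With equal standard deviations and r of 0.3, 0.5 or 0.7, the unadjusted analysis gives up the equivalent of roughly 12, 8 or 3 patients per arm. The figure moves in either direction with the ratio of the standard deviations and should not be quoted without its assumptions. The gain does not extend to the Rauschning and Lindgren grade or to any comparison of proportions. The change is worth making before data are analysed, but the planned comparison is not invalid without it.

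**What to change.** In section 4.II, replace the t-test of change scores for continuous outcomes with a linear model of the week-24 value on randomised arm and the baseline value of the same measure. Apply it to VAS, to each KOOS subscale, and to cyst size if its dimensions are recorded at the baseline ultrasound; section 4.I should say whether they are. Report the adjusted PRP-minus-corticosteroid difference with a 95% confidence interval. This also removes the ambiguity of a matched test between independent arms.

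Keep cyst size on its measured scale, or use a transformation that allows zero. A fully resolved cyst has no logarithm, and section 2.II cites complete disappearance in about 7% of patients after joint aspiration and corticosteroid injection.

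A mixed model using weeks 12 and 24 together may be added, so that a patient who misses one follow-up visit still contributes. If so, name the week-24 contrast as the main estimate.

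The cost is a few sentences of analysis text and one degree of freedom per model. No new data, visits or patients are needed for VAS and KOOS. Cyst size needs only that the dimensions be recorded at the ultrasound already scheduled.
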